1.1 Background

1.1.1 Study design

This is a randomized, multi-center, evaluator-blinded, no-treatment controlled study of Restylane Defyne for correction of Chin Retrusion. Eligible subjects will be randomized either to the Treatment group or the Control Group in a 3:1 ratio.

Each subject assigned to the Treatment Group will receive an initial treatment on Day 1. A touch-up treatment may be performed 4 weeks after the initial treatment if optimal chin augmentation has not been obtained.

Subjects assigned to the Control Group will not receive treatment at baseline but will return for routine follow-up. At month 6 visit after randomization the subjects in the Control Group will be offered a treatment and an optional touch-up treatment 4 weeks later.

1.1.2 Number of subjects and randomization

Approximately 148 subjects will be randomized in a 3:1 ratio to treatment with Restylane Defyne or to no-treatment Control Group. The randomization will be stratified by center.

1.2 Study objectives

1.2.1 Primary effectiveness objective

[figure not shown]
The primary objective is to measure the effectiveness of Restylane Defyne versus a no-treatment control in the treatment of Chin Retrusion by comparing the percentage of responders, defined by at least 1 point improvement from baseline on the Galderma Chin Retrusion Scale (GCRS), as measured by the Blinded Evaluator at 6 months (after last treatment in Treatment Group, and after randomization in Control Group).

1.2.2 Secondary effectiveness objectives

The secondary objectives are:

- Percentage of responders, defined by at least 1 point improvement from baseline on the GCRS, as measured by the Blinded Evaluator at 3, 9 and 12 months after last treatment in Treatment Group, and at 3 months after randomization as well as 3, 6, 9 and 12 months after the last treatment in Control Group.
- Percentage of responders, defined by at least 1 point improvement from baseline on the GCRS, as measured by the Treating Investigator at each follow-up visit

CCI

CCI

1.2.3 Safety objectives

The safety objectives are:

- Incidence, intensity, duration and onset of adverse events (AEs) collected throughout the study

CCI

1.3 Effectiveness assessments

For all assessments, baseline will be defined as the observation that is closest to but prior to study treatment on Day 1. Likewise, change from baseline will be calculated as the value at a given time point minus the baseline value.

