4.4.2 Blinding

Only the evaluator will be blinded to treatment.

The Blinded Evaluator shall not be allowed to retrieve study supplies or to be present during opening of the study supplies or injections. The Treating Investigator or the subjects are not allowed to discuss treatments with the Blinded Evaluator. All documents with information on study products and randomization assignment shall be kept in a separate binder not available to the Blinded Evaluator.

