4.4.3 Emergency unblinding

Not applicable as the Treating Investigator is unblinded.

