**CCI**

| | | | | | | |
|---------------------|---|---|---|---|---|---|
| Device deficiencies | | X | X | | | |
| Assessment of AE | X | X | X | X | X | X |
| Study termination | | | | | | X |

- a) Screening visit and baseline visit can be combined to one visit if feasible.
- b) This visit is only for subjects who receive touch-up (If no touch-up performed, subjects will conduct the 4w after last treatment visit).
- c) Prior to randomization.
- d) Prior to treatment.
- e) Only performed at 6M.
- f) Only performed at early termination if termination occurs before 6 months visit after last treatment.
- g) Only performed at CCI 6M.
- h) Serum pregnancy test (S-HCG).
- i) Urine pregnancy test (U-HCG).
- j) Only performed if the screening S-HCG was done \geq 2 weeks before baseline.

Table 2. Schedule of Events for Control Group

| Activity | Control Group | | | | | | | | | |
|---------------------------------------|------------------------|-----------------------|-----------------------------------|------------------------------------|-----------------------------------|----------------------------------|------------------------------------|---|--------------------------------------|--|
| | Screening ^a | Baseline ^a | Follow-up | Follow-up | Follow-up /Treatment | Optional Touch-up ^b | Follow-up | Follow-up | Final visit / Early termination | |
| | D-21 to 1 | D1 | 4W(\pm 3d) after randomization | 3M (\pm 1w) after randomization | 6M(\pm 1w) after randomization | 4W(\pm 3d) after 6M treatment | 4W(\pm 3d) after last treatment | 3M (\pm 1w), 6M(\pm 1w) and 9M (\pm 2w) after last treatment | 12M (\pm 2w) after last treatment | |
| Informed consent | X | | | | | | | | | |
| Demography | X | | | | | | | | | |
| Medical history & concurrent diseases | X | X | | | | | | | | |
| Concomitant medication/procedures | X | X | X | X | X | X | X | X | X | |
| Vital signs | | X ^c | | | X ^d | | | | | |
| Laboratory tests | X | | | | X ^d | | | X ^e | X ^f | |

| | | | | | | | | | |
|----------------------------------|----------------|--------------------|---|---|------------------|------------------|---|---|----------------|
| ECG | X | | | | | | | | |
| Pregnancy test | X ^g | X ^{c,h,i} | | | X ^{d,h} | X ^{d,h} | | | X ^h |
| Inclusion and Exclusion criteria | X | X | | | | | | | |
| Randomization | | X | | | | | | | |
| Treatment | | | | | X | X | | | |
| GCRS(Blinded Evaluator) | X | X | | X | X ^d | | | X | X |

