4.8 Visits

4.8.1 Visits for Treatment Group

4.8.1.1 *Screening (D-21 to D1)*

- Informed consent
- Demography (Initials, Date of birth, Gender and Ethnic origin)
- Screening laboratory tests (haematology and serum chemistry)
- S-HCG for childbearing potential women
- ECG
- Inclusion and exclusion criteria
- GCRS (by Blinded Evaluator and Treating Investigator)
- Medical history/concurrent diseases including prior facial dermatological procedures performed, and fillers or implants used
- Concomitant medications/procedures
- AE during the visit

4.8.1.2 *Baseline (D1)*

- Medical history/concurrent diseases
- Vital signs (pulse rate, blood pressure, respiratory rate, body temperature)
- Inclusion and exclusion criteria
- U-HCG for childbearing potential women (Only performed if the screening S-HCG was done ≥ 2 weeks before baseline)
- Photography (before injection)
- Randomization
- GCRS (by Blinded Evaluator and Treating Investigator)
- Treatment

CCI

- Concomitant medications /procedures
- Device deficiencies
- AE since last visit

4.8.1.3 *Optional Touch-up 4W ($\pm 3d$) after randomization (only for subjects who receive touch-up)*

- Photography (before injection)
- GCRS (by Treating Investigator)

CCI

- U-HCG for childbearing potential women (before injection)
- Treatment

CCI

- Concomitant medications/procedures
- Device deficiencies
- AE since last visit

| | | |
|--|--|---------------------------|
|  | Title 43CH1627 Clinical Study Protocol | Doc id MA-34970 |
|--|--|---------------------------|

4.8.1.4 4W ($\pm 3d$) after last treatment

- Photography
- GCRS (by Treating Investigator)

CCI

- Concomitant medications /procedures
- AE since last visit

4.8.1.5 3M ($\pm 1w$), 6M ($\pm 1w$) and 9M ($\pm 2w$) Follow-up after last treatment

- Photography
- GCRS (by Blinded Evaluator and Treating Investigator)

CCI

- Concomitant medications /procedures
- AE since last visit
- Laboratory tests (Only performed at 6M)

4.8.1.6 12M ($\pm 2w$) after last treatment Final visit or Early termination

- Photography
- GCRS (by Blinded Evaluator and Treating Investigator)

CCI

- U-HCG for childbearing potential women
- Concomitant medications/procedures
- AE since last visit
- Laboratory tests (Only performed at early termination if termination occurs before 6 months visit after last treatment)
- Study termination

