5.2 Inclusion Criteria

The subject must meet the following criteria to be eligible for the study:

1. Signed and dated informed consent to participate in the study.
2. Men or women aged 18 years of age or older of Chinese origin.
3. Subjects seeking augmentation therapy for chin retrusion.
4. GCRS score of 1 or 2 as assessed by the Blinded Evaluator.

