2.4.4 Secondary effectiveness analysis

- *Percentage of responders as measured by the Blinded Evaluator at 3, 9 and 12 months after last treatment in Treatment group and at 3 months after randomization as well as 3, 6, 9 and 12 months after last treatment for control group*

The percentage of responders will be calculated at each time point and analyzed descriptively. At 3 months after last treatment for Treatment group and after randomization for Control group Fishers' Exact test will be used to compare the responder rates.

- *Percentage of responders as assessed by the Treating Investigator at each follow-up visit*

The percentage of responders will be calculated at each time point. At Week 4, Month 3 and Month 6 after last treatment for Treatment group and after randomization for Control group Fishers' Exact test will be used to compare the responder rates.

CC1

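### Baseline GCRS need not be scored before randomization, so the unblinded Treating Investigator may score it knowing the arm, which exposes that rater's three between-arm tests to avoidable bias

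*SAP*

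**What the plan says.** SAP 1.3 sets one baseline rule for every assessment: "For all assessments, baseline will be defined as the observation that is closest to but prior to study treatment on Day 1". The rule does not mention randomization.

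The Treatment Group schedule in Protocol 4.7 has two timing footnotes for Day 1. One is "c) Prior to randomization", attached to vital signs and the pregnancy test. The other is "d) Prior to treatment", and it is the only timing footnote on baseline GCRS, for both raters. The Control Group schedule also puts vital signs and the pregnancy test before randomization, but its baseline GCRS entries carry no timing footnote.

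The two raters are placed differently:

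- **Blinded Evaluator.** Inclusion criterion 4 (Protocol 5.2) requires a "GCRS score of 1 or 2 as assessed by the Blinded Evaluator". Protocol 4.4.2 keeps the allocation from this rater: "The Treating Investigator or the subjects are not allowed to discuss treatments with the Blinded Evaluator".
- **Treating Investigator.** Protocol 4.4.3 says of emergency unblinding: "Not applicable as the Treating Investigator is unblinded". Protocol 4.4.1 has this rater hold the treatment information. This rater's GCRS is not an eligibility criterion.

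A responder improves by at least one point from baseline. SAP 2.4.4 compares Treating Investigator responder rates between arms by Fisher's exact test at these times: "At Week 4, Month 3 and Month 6 after last treatment for Treatment group and after randomization for Control group". SAP Table A 22 is laid out for those three tests.

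**The concern.** Response is a change score, so the baseline is half of the outcome. If the rater knows the arm when scoring it, baselines can differ systematically between arms before anyone has been injected, and randomization no longer protects the comparison.

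GCRS has four grades and response needs one, so a baseline error of one grade equals the whole responder threshold. A treated subject scored 2 instead of 1 on Day 1, and then 1 at follow-up, is a responder without any change in the chin. A control scored 0 by this rater cannot respond at all.

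The SAP rule makes this worse. The Treating Investigator also scores GCRS at screening, but the rule picks the latest score before treatment, so a Day 1 score made after allocation replaces the screening score.

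At stake is the credibility of a named secondary endpoint. Open-label follow-up scoring by this rater is built into the design; an open-label baseline is not.

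**Working it through.** **1. Is a score before randomization required anywhere?**

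| Day 1 item | Treatment Group schedule | Control Group schedule |
|---|---|---|
| Vital signs | before randomization | before randomization |
| Pregnancy test (if due) | before randomization | before randomization |
| GCRS, Blinded Evaluator | before treatment | no timing |
| GCRS, Treating Investigator | before treatment | no timing |

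Protocol 8.2 repeats the rule for the pregnancy test. Neither document contains such a rule for the Day 1 GCRS. The visit lists in Protocol 4.8.1.2 and 4.8.2.2 name Randomization immediately before GCRS. That is compatible with late scoring but does not prove it, because the lists are not stated to be chronological.

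**2. Which rater is exposed?** Criterion 4 forces a Blinded Evaluator score before randomization, and the blind covers any later Day 1 score. Neither safeguard applies to the Treating Investigator.

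**3. Which analyses does it reach?** GCRS between-arm Fisher comparisons in SAP 2.4.3 and 2.4.4, not counting repeats on the PP set or with hot deck imputation:

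- Blinded Evaluator: Month 6 (primary) and Month 3 = 2
- Treating Investigator: Week 4, Month 3 and Month 6 = 3
- Total 2 + 3 = 5, of which 3 rest on the Treating Investigator's baseline.

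**4. The visible sample-size arithmetic.** 111 + 37 = 148 and 111/37 = 3, as stated. With 15% dropout, 111 × 0.85 = 94.35 and 37 × 0.85 = 31.45, so about 94 and 31 remain. The assumed response rates are redacted, so the sample size itself cannot be rebuilt, and this point does not depend on it.

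**5. Sensitivity of one test to a shift (illustration only).** The documents give no rates, so these are assumptions: no true effect, control response p0 from 5% to 30%, and a fraction b of treated non-responders turned into responders by arm-aware baseline scoring. Then

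p1 = p0 + b(1 − p0).

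For p0 = 0.10 and b = 0.10, p1 = 0.10 + 0.10 × 0.90 = 0.19. Summing the two binomial distributions over all tables where a two-sided Fisher test gives p < 0.05 yields these rejection probabilities:

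| b | 111 vs 37, p0 = 10% | 111 vs 37, p0 = 5–30% | 94 vs 31, p0 = 5–30% |
|---|---|---|---|
| 0 | 3.5% | 2.6–3.9% | 2.4–3.8% |
| 5% | 7.1% | 5.6–7.3% | 4.6–6.0% |
| 10% | 19.4% | 10.3–28.6% | 7.9–21.8% |
| 20% | 61.9% | 28.8–78.8% | 22.8–70.2% |

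With no shift the test stays within 5%. The other rows show what a given shift would do; nothing in the documents says that any of these values of b occurs.

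**6. A related wording gap.** Controls receive no treatment on Day 1, so the SAP 1.3 rule does not literally give them a baseline. Table A 31 labels their baseline as the randomization visit, so the intent is clear.

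**The case against.** The strongest reply is that these comparisons are open-label anyway. The Treating Investigator injects, holds the allocation and makes every follow-up score, so even a perfect baseline leaves the three p-values open to rater bias. None of them decides the trial: SAP 2.4.3 ties success to the Blinded Evaluator's Month 6 endpoint alone. This stands, and it limits the point to one additional, removable source of bias in secondary analyses.

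The order of the visit lists is weak evidence. The screening list puts the eligibility criteria before the GCRS that criterion 4 needs, so the lists are plainly not sequences. This also stands. The finding rests on the missing timing requirement, not on the order.

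There are partial safeguards. The Treating Investigator's screening score is on record, the scale uses anatomical reference lines and a photo guide, and photographs are taken at baseline. They limit arm-driven rescoring without excluding it. Where screening and baseline are one visit, which Protocol 4.7 allows, there may be no separate earlier score.

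Finally, the SAP does not say in words that Treating Investigator response is measured from that rater's own baseline, and Table A 8 reports only the Blinded Evaluator's baseline. The own-baseline reading is still the natural one for improvement as measured by the Treating Investigator. None of these replies supplies the missing requirement.

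**Conclusion.** The concern holds. The plan lets an unblinded rater score baseline after learning the allocation, and its baseline definition would use that score in 3 of the 5 GCRS between-arm Fisher comparisons. No size of bias is claimed, because the documents give nothing from which to derive one; the rejection probabilities above depend on assumed shifts.

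The conclusion assumes that each rater's response uses that rater's own baseline, and that a Day 1 score, where one exists, takes precedence over screening. The primary endpoint is not shown to be biased while the Blinded Evaluator's blind holds. This should be corrected because it is avoidable at almost no cost, not because it threatens the main result.

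**What to change.** - **Protocol 4.7:** give baseline GCRS the before-randomization footnote, for both raters and in both schedules. For the Blinded Evaluator this is for uniformity.
- **Protocol 4.8.1.2 and 4.8.2.2:** list GCRS above Randomization. This helps clarity but would not be sufficient without the footnote.
- **SAP 1.3:** define baseline GCRS as the last score before randomization. This also gives controls an explicit baseline. State that each rater's response is measured from that rater's own baseline.
- **If baselines are already collected:** add a sensitivity analysis of Treating Investigator response using that rater's screening GCRS, which is recorded in both arms. Report by arm how many subjects had screening and baseline combined, since they may have no separate earlier score.
- **In the report:** say that this deals only with the baseline and does not remove bias from the same rater's open-label follow-up scores.

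The cost is a footnote change, a reordering within one visit and a short SAP edit. The sensitivity analysis uses existing data. No new visit, assessment or rater is needed.

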1.4.2 Secondary effectiveness endpoints

Secondary effectiveness endpoints include:

- (i) **Percentage of responders as measured by the Blinded Evaluator at 3, 9 and 12 months after last treatment in Treatment group and at 3 months after randomization as well as 3, 6, 9 and 12 months after last treatment in Control group**

A responder is defined as a subject who achieves a score of at least 1 point improvement from baseline on the GCRS.

 GALDERMA	Title Statistical Analysis Plan 43CH1627 - Chin	Doc id MA-38115
--	---	---------------------------

(ii) Percentage of responders as assessed by the Treating Investigator at each follow-up visit

The follow-up assessments will be done 3 months, 6 months, 9 months and 12 months after last treatment for the Treatment Group, and at 3 months and 6 months after randomization as well as 3 months, 6 months, 9 months and 12 months after last treatment for Control Group.

A responder is defined as a subject who achieves a score of at least 1 point improvement from baseline on the GCRS.

CCI

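### Control's responder rates after its Month 6 injection are measured from Day 1, so six months of untreated change is mixed into the apparent device response

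*SAP*

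**What the plan says.** SAP 1.3 gives a single rule for every assessment: the baseline is the observation "closest to but prior to study treatment on Day 1". It continues that "change from baseline will be calculated as the value at a given time point minus the baseline value". No exception for Control is visible.

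SAP 1.1.1 states that "Subjects assigned to the Control Group will not receive treatment at baseline". Control's first injection comes later: "At month 6 visit after randomization the subjects in the Control Group will be offered a treatment and an optional touch-up treatment 4 weeks later".

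SAP 1.4.2 defines a responder by at least one point of improvement from baseline. For Control it applies this to the Blinded Evaluator's ratings "at 3 months after randomization as well as 3, 6, 9 and 12 months after last treatment in Control group". The Treating Investigator endpoint covers the same post-injection visits. Tables A 24 and A 25 hold these Control rows. Their notes repeat the one-grade-from-baseline definition and mention the optional Month 6 treatment, but they do not move the baseline.

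The Control schedule of events and Protocol 4.8.2.5 have both raters score the GCRS at the Month 6 visit. The schedule marks those scores as taken before treatment.

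**The concern.** For Control, the follow-up clock restarts at the injection but the reference value does not. A control rated one grade better at Month 6, untreated, who keeps that grade is counted as a responder after last treatment even if the injection added nothing. A control rated one grade worse at Month 6 who then gains exactly one grade from the injection is counted as a non-responder. In the Treatment Group the reference is taken just before the first injection, so a post-treatment rate there does not carry this six-month gap.

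At stake is how the Control post-injection rows are read. They belong to named secondary endpoints in a study that Protocol 2.5 intends for registration, and readers will naturally take them as further evidence of device response.

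**Working it through.** **1. Which Control baseline is meant.** Read literally, SAP 1.3 does not fit an arm with no Day 1 treatment. Protocol 4.8.2.2 names a Control baseline visit on Day 1 with GCRS by both raters, and SAP Table A 31 labels Control's baseline row as randomization. The Day 1 rating is therefore meant.

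**2. Which analyses are affected.** The primary comparison (SAP 2.4.3) and the Fisher tests at Week 4, Month 3 and Month 6 (SAP 2.4.4) use Control ratings timed from randomization and taken before any Control injection. Day 1 is correct for all of them. The affected outputs are Control's rows at 3, 6, 9 and 12 months after last treatment in Tables A 24 and A 25.

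**3. Age of the reference.** Control's Day 1 rating is about 6 months old (window ±1 week) at injection. At the four post-injection visits it is about 6+3 = 9, 6+6 = 12, 6+9 = 15 and 6+12 = 18 months old, plus about 4 weeks if there was a touch-up.

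**4. Number of controls.** The SAP's split reproduces: 148 × 1/4 = 37 Control and 148 × 3/4 = 111 Treatment. After 15% dropout, 37 × 0.85 = 31.45, about 31 evaluable. The concern does not depend on these figures; they only turn percentages into subjects.

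**5. Illustrative size.** The documents give none of these inputs, so all are assumed:
- u, w: proportions of controls one grade better or worse at Month 6, untreated. Each is varied over 0, 5%, 10% and 20%, and improvers are taken to hold their grade.
- p = 0.80: chance of gaining at least one grade from the pre-injection rating.
- p2 = 0.20: chance of gaining at least two.
- s = 0.5: share of untreated improvers with room to improve again.

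Formulas:
- Day 1 baseline: u + (1-u-w)p + w·p2
- Month 6 baseline: u·p·s + (1-u-w)p + w·p
- Difference: u(1 - p·s) - w(p - p2) = 0.60u - 0.60w

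At u = 10%, w = 0, the Day 1 rate is 0.10 + 0.90 × 0.80 = 0.82. The Month 6 rate is 0.10 × 0.80 × 0.5 + 0.90 × 0.80 = 0.76.

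| u | w | Day 1 baseline | Month 6 baseline | Difference (points) |
|---|---|---|---|---|
| 5% | 0 | 81% | 78% | +3 |
| 10% | 0 | 82% | 76% | +6 |
| 20% | 0 | 84% | 72% | +12 |
| 0 | 5% | 77% | 80% | -3 |
| 0 | 10% | 74% | 80% | -6 |
| 0 | 20% | 68% | 80% | -12 |
| 10% | 10% | 76% | 76% | 0 |

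The exact cancellation in the last row is particular to p = 0.80. Keeping p2 = p/4 and u = w = 10%, the difference is +2.5 points at p = 0.60 and -1.25 at p = 0.90.

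**6. Zero-effect check.** With p = p2 = 0, the Day 1 baseline reports a responder rate of u and the Month 6 baseline reports 0. At u = 10% that is 37 × 0.10 = 3.7 of 37 controls, or 3.1 of 31, counted as responders to an injection that did nothing.

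**The case against.** The strongest reply is that little depends on this. Success rests on the primary p-value alone, the planned Fisher tests are untouched, and Table A 24 has neither a difference row nor a p-value column. All of that stands and keeps the point minor.

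A reader might infer that Control has no defined baseline, so that the primary responder rate is in doubt. The documents do not support that: the Day 1 visit and the label in Table A 31 identify the baseline. Only the wording of SAP 1.3 is loose.

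A reader might also infer that the Month 6 pre-injection rating goes unused. It does not. The Blinded Evaluator's rating is the Control half of the primary endpoint (Table A 17), and its grade distribution appears in Table A 31. What is missing is the within-subject change from it to the later visits.

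A further objection is that moving the baseline would alter the endpoint in Protocol 3.2.2, which covers Control visits before and after injection in one definition, and would contradict SAP 2.8, which declares no changes. That is a good reason to add a rate rather than replace one.

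Finally, a Month 6 baseline has limits of its own. Some controls may be rated 0 or 3 by then, although Protocol 5.2 admits only 1 or 2. The rating also carries error, as the Treatment Group's Day 1 rating does. Re-anchoring removes the six-month gap; it does not make the reference error-free.

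**Conclusion.** The point holds for Control's descriptive post-injection responder rates and for nothing else. Followed as written, the plan measures them from a rating about six months older than the injection, so they combine device response with untreated change and rating variation.

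It is tempting to conclude that the plan overstates the device. The documents do not support a direction: untreated improvement inflates the rate, untreated worsening deflates it, and the two roughly cancel when balanced. Nor do they support a size. The ±3 to ±12 points shown rest wholly on assumed inputs, and the upward part shrinks if Month 6 improvements are rating noise that does not persist. If almost no control changes grade untreated, there is almost no effect.

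Parts of the SAP are redacted and could hold a further rule, but the visible one is stated for all assessments. SAP 2.5.2 already counts adverse event onset from the most recent treatment; effectiveness has no visible counterpart. The point is minor, but cheap to put right.

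**What to change.** 1. Reword SAP 1.3 so that baseline is the same rater's last GCRS before randomization or Day 1 treatment in both arms (for Control, the Day 1 visit rating). Use it for the randomized comparison.
2. For Control visits after the Month 6 injection, add to Tables A 24 and A 25 the responder rate from the same rater's pre-injection Month 6 GCRS. Keep the Day 1-based rate as the protocol-defined endpoint, and base any statement about device effect in treated controls on the added rate.
3. Footnote the number of controls rated 0 before injection, who cannot respond, and the number rated 3, who are outside the eligible range. List the addition in SAP 2.8.

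The cost is one derived variable from ratings already collected, a few extra table rows, and possibly a small number of controls who cannot count as responders on the added rate. Protocol 3.2.2 is unchanged.
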